6.4 STATISTICAL ANALYSES

6.4.1 General Approach

For descriptive statistics, categorical data will be presented as percentages. Continuous data will be presented as means with standard deviations and ranges. For inferential statistics, statistical significance will be declared if $\alpha=0.05$ and tests will be two-tailed; results will be interpreted in the context of a pilot study in which statistical testing is for descriptive purposes. For exploratory analyses, checks of assumptions will be conducted and corrective procedures will be applied accordingly (e.g., transformation of non-normal data or nonparametric tests will be substituted).

6.4.2 Analysis of the Primary Endpoints

Planned analysis: For the primary feasibility aim, descriptive and summary statistics will be used to report parent and child rates of intervention completion, as well as ratings of satisfaction with the intervention via responses on a feasibility questionnaire. A Z-test for binomial proportion with continuity correction will be used to examine whether the retention rate and at-home practice compliance rate are lower than the target (i.e., respectively, a target of 70% participants retained over 8 weeks and a practice rate of 4 out of 7 days per week on average over 8 weeks). Retention rate will be evaluated across the experimental and control groups, and separately for each. In addition, descriptive and summary statistics will be used to detail the total number of patients screened, determine rates and reasons for non-eligibility and patient refusal, the number and type of adverse events (if any), and the number of days practiced (obtained via text/email) by each participant. A series of t-tests (for continuous variables) and Chi-square tests (for non-continuous variables) will be used to examine potential differences between eligible patients who accept or decline study participation; between participants who meet (versus do not meet) the target practice rate (i.e., 4 out of 7 days completed); and for other medical, psychological, and contextual factors. Nonparametric models will be used if data do not meet assumption checks.

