1 INTRODUCTION

1.1 STUDY OBJECTIVES

1.1.1 Primary Objective

To assess the feasibility and acceptability of an enhanced mindfulness intervention in children (ages 5-17) and young adults (ages 18-24) with a high-grade or high risk cancer and one of their primary caregivers. Feasibility and acceptability will be evaluated based on the following:

- A. Proportion of eligible dyads who enroll during a two-year period
- B. Treatment specific retention among all randomized participants, with a target retention rate of 70% over the 8 week EMI/control period
- C. Compliance with at-home practices, with a proposed target rate of 4 out of 7 days per week on average over the 8 week EMI period
- D. Parent and patient reports of satisfaction on the feasibility questionnaire; for youth ages 8+ and caregivers, average item scores >3.0 will be deemed to reflect adequate feasibility

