Approximately one week and three weeks after the initial in-person training session, a brief (i.e., 30 minute) follow-up sessions will take place with the two-person research team. We anticipate that the majority of participants in this study will be staying at or nearby the NIH during this time period, or will be visiting the NIH frequently (e.g., receiving radiation treatment through other protocols at the NIH Intramural Research Program), which will make it possible to schedule follow-ups in person. For in-person follow-up, caregivers and children will each meet separately with their mindfulness coach, and then come together at the end of the follow-up for a joint meeting. If participants are not available for an in-person follow-up, sessions will take place via video chat (e.g., Skype, FaceTime) or telephone if video chat is unavailable. The literature suggests comparable efficacy between in person and teletherapy, which makes this a valid option [55](#). The purpose of these follow-up sessions is to troubleshoot any challenges that arise (e.g., difficulty finding time to practice) and to engage in a clinician-guided practice. Depending on the age and functional limitations of the child, remote follow-up sessions will take place jointly with the parent/child or separately. Attendance in follow-up sessions will be systematically tracked and will be evaluated as part of the feasibility of this intervention.

Throughout the intervention, weekly text messages (or emails when text is not an option) will be sent to parent participants and youth with a personal cell phone, in which we will ask individuals to indicate the number of days practiced in the past week. The following script will be used as a guideline: "Hello. Just checking in to ask how many days you have practiced mindfulness over the past week (since **INSERT DATE**). Please reply by text (or email) with your response." The weekly interval will mitigate concerns regarding inaccurate recall [56:57](#), without overburdening families. Among younger children who do not have a personal cell phone, compliance data will be collected through parents, or children (>7 years old) will be loaned an iPod (with parental permission) from the study team through which compliance data can be obtained. All participants will also be provided with an optional tracking sheet, on which they can keep track of practice days and note the specific exercises completed (Study Instrument 3).

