3.3.4 Home-Based Mindfulness Practices for Children (5-7 years old)

Mindfulness practices for young children are interactive and engaging. These exercises are intentionally game-like and utilize reinforcers (e.g., tangible items, positive caregiver attention) to help sustain participation and patient enjoyment. Tangible reinforcers (e.g., stickers) will be provided in the mindfulness toolkit. All exercises should be completed with a caregiver and offer mutual benefit such that a caregiver would not have to complete a separate practice. Descriptions of these exercises are in Study Instrument 7.

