6 STATISTICAL CONSIDERATIONS

6.1 STATISTICAL HYPOTHESIS

The current protocol is a pilot study, and therefore its primary aim does not include hypothesis testing. Components of feasibility (as described in section **6.1.1**) will be evaluated during the recruitment phase (i.e., proportion of eligible dyads who enroll) and following the 8-week EMI/psychoeducation period.

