6.1.1 Primary Objective

The primary objective of this study is to assess the feasibility and acceptability of an enhanced mindfulness intervention in children and young adults (ages 5-24) with a high-grade or high-risk cancer and one of their primary caregivers. Feasibility and acceptability will be evaluated based on the following:

1. Proportion of eligible dyads who enroll during a two-year period
2. Treatment specific retention among all randomized participants, with a target retention rate of 70% over the 8 week EMI/control period
3. Compliance with at-home practices, with a proposed target rate of 4 out of 7 days per week on average over the 8 week EMI period
4. Parent and child reports of satisfaction on the feasibility questionnaire; for youth ages 8+ and caregivers, average item scores >3.0 will be deemed to reflect adequate feasibility

Of note, because the sample size of this study is very limited, even the results of the comparisons tested using statistical methods and identified within the primary objective will be considered descriptive and hypothesis generating.

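### The binomial Z-test of at-home practice names no unit: with days as trials it ignores within-person correlation, and with persons as trials it has no stated null

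*Combined protocol and SAP*

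**What the plan says.** Section 6.4.2 (Analysis of the Primary Endpoints) applies one test to two quantities: "A Z-test for binomial proportion with continuity correction will be used to examine whether the retention rate and at-home practice compliance rate" fall below target. For retention, the unit (participants) and the null (70%) are both given. For practice the target is "a practice rate of 4 out of 7 days per week on average over 8 weeks". Section 1.1.1 states it the same way, "with a proposed target rate of 4 out of 7 days per week on average over the 8 week EMI period", and section 6.1.1 repeats it. The 70% is tied to retention alone by the word respectively, so it cannot be borrowed for practice.

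Section 6.4.2 also compares groups "between participants who meet (versus do not meet) the target practice rate (i.e., 4 out of 7 days completed"), but only to look for factors associated with practice. No section says what share of participants should meet the target.

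The data come from weekly messages (section 3.2.1) "in which we will ask individuals to indicate the number of days practiced in the past week", so each person has up to 8 replies covering 56 days. For ages 5-7, section 3.3.4 lets child and caregiver share one practice: "All exercises should be completed with a caregiver and offer mutual benefit such that a caregiver would not have to complete a separate practice".

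Section 6.4.1 sets two-tailed tests at 0.05. Section 6.1 says: "The current protocol is a pilot study, and therefore its primary aim does not include hypothesis testing". Section 6.1.1 adds that "even the results of the comparisons tested using statistical methods and identified within the primary objective will be considered descriptive and hypothesis generating".

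**The concern.** A binomial test needs a trial and a null proportion. For practice the plan gives neither explicitly, and each natural reading fails for a different reason.

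The target is a mean number of days, so days are the obvious trials and 4/7 the obvious null. The binomial variance then assumes that every participant practises at the same underlying rate. The plan itself expects some people to reach the target and others not. With about 10 people per role in the enhanced mindfulness intervention (EMI) arm, the real information is close to 10 observations, not 560.

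If each participant is classed as meeting the target or not, the inflation disappears. The test then has no stated null and no longer addresses a mean.

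At stake is a p-value for a primary feasibility component that could report practice as below target when the data cannot show that. Section 1.2.3 plans a larger trial once feasibility is established, so the signal would be read.

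**Working it through.** **Inputs from the documents.** 10 dyads in the EMI arm (sections 2.6 and 3.1); 8 weeks × 7 days = 56 days per person; target 4/7 = 0.571; two-tailed 0.05 (section 6.4.1). Section 6.2 gives no sample size calculation, so there is no planned figure to reproduce. The documents give no within-person correlation; the ICC range 0.01 to 0.5 is an assumption.

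**Days as trials: the rejection limit.** For 10 people of one role, N = 10 × 56 = 560 and the expected count is 560 × 4/7 = 320.
- Standard error in days per week: 7 × √[(4/7)(3/7)/560] = 0.146.
- Standard deviation of the count: √[560 × (4/7)(3/7)] = 11.71.
- The corrected two-sided test rejects on the low side when the count is below 320 − 0.5 − 1.96 × 11.71 = 296.5. That is 296 days or fewer, or 296/560 × 7 = 3.70 days per week.
- With 7 people (70% of 10), N = 392, the standard error is 0.175 and the limit is 204 days, or 3.64 per week.

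**Days as trials: actual error.** Person-level rates were drawn from a beta distribution with mean exactly 4/7, then 56 days per person, in 200,000 simulated trials. Design effect = 1 + 55 × ICC. Between-person SD = 7 × √[ICC × (4/7)(3/7)] days per week.

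| ICC (assumed) | Between-person SD | Design effect | Z-test, false below target | Z-test, two-sided error | t-test on person means, two-sided error |
|---|---|---|---|---|---|
| 0.01 | 0.35 | 1.55 | 5% | 11% | 5.1% |
| 0.02 | 0.49 | 2.1 | 8% | 17% | 5.0% |
| 0.05 | 0.77 | 3.75 | 15% | 30% | 5.1% |
| 0.1 | 1.10 | 6.5 | 21% | 43% | 5.1% |
| 0.2 | 1.55 | 12 | 28% | 57% | 5.4% |
| 0.5 | 2.45 | 28.5 | 35% | 71% | 5.7% |

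At ICC 0 the Z-test gives about 4.5% two-sided and 2.3% on the low side, so the excess comes from the correlation. With 7 people, false findings below target are 6% to 35%. The lower tail of the person-level t-test is 2.0% to 2.4% at n = 10.

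**Persons as trials.** Suppose 4 of 10 people meet the target. The corrected Z is (|4 − 10q| − 0.5)/√[10q(1 − q)], where q is the unstated target share.
- q = 50%: p = 0.75
- q = 4/7: p = 0.44
- q = 70%: p = 0.08
- q = 80%: p = 0.006

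The same result can be unremarkable or strongly significant. The question also changes: in the simulation, with a true mean of exactly 4, only 53-55% of persons have an observed mean of 4 or more.

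**One data set, two answers (invented, with a spread close to that implied by ICC 0.1).** Ten people practise 5, 5, 4.5, 4, 4, 3.5, 3.5, 2.5, 2.5 and 1.5 days per week: mean 3.6, SD 1.15.
- Days as trials: 36 × 8 = 288 of 560 days; (|288 − 320| − 0.5)/11.71 = 2.69, p = 0.007.
- Person means: (3.6 − 4)/(1.15/√10) = −1.10, p = 0.30, 95% CI 2.8 to 4.4.

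**The case against.** The strongest objection is that little depends on this p-value. The plan disclaims hypothesis testing for its primary aim, calls the tests descriptive, summarises the days practised by each participant (section 6.4.2) and lists individual data (section 6.4.4). A reader could see the spread between people, and no go/no-go rule uses the test. This stands and limits the harm. It does not supply the missing unit or null, and section 6.4.1 still declares significance at 0.05.

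The size of the error rests on an assumed ICC, and 0.5 is an extreme case on a 0-7 day scale. That is fair. But an ICC of 0.01 already doubles the low-side error. Because section 6.4.2 asks only whether practice is lower than target, the low-side column is the relevant one; the two-sided totals matter only under the two-tailed rule.

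The person-level p-values use target shares that no document gives for practice. True, and that is the point: without a stated share the result is undetermined. A person-level test could be made valid by stating a share and using an exact binomial interval, but it would answer a different question from the stated target.

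The fallback to nonparametric models in section 6.4.2 follows the t-tests and Chi-square tests. Even read broadly, it names no unit and does not deal with repeated days.

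Finally, missing weekly replies are a separate matter from the choice of unit. They come into the fix only because a person's mean cannot be computed without a rule for them.

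**Conclusion.** The concern holds. The practice test cannot be run as written without an unstated choice of unit, and neither choice gives a usable test of the stated target. With days as trials, the only reading with a stated null, false findings of practice below target occur 5% to 35% of the time against 2.5% nominal. This assumes 10 people with complete reporting, a true mean of exactly 4 and an ICC of 0.01 to 0.5. With persons as trials there is no null.

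It should be fixed, but the consequence is bounded: the observed mean is not biased by the choice of test, no formal decision rests on the p-value, and the plan labels it descriptive. The retention test is not affected by this point.

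**What to change.** In section 6.4.2, drop the Z-test for practice and state instead:
- Each EMI participant's mean days per week is computed from the weekly replies. The mean of these is reported with a one-sample t-based 95% CI and compared with 4.
- Patients and caregivers are analysed separately. If they are ever pooled, dyad means are used, since practice may be shared at ages 5-7.
- The number of the 8 weeks with a reply is reported for each person. The analysis is repeated with unreported weeks counted as 0 days, as a lower bound. This version also includes anyone who never replies, in line with section 6.3, which keeps all randomized participants.
- An interval that includes 4 does not show that the target was met.

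The cost is a change of wording, one extra summary and one repeat analysis; the weekly replies are already collected. The interval becomes wider. At n = 10 the average half-width is about 0.4, 0.5, 0.6, 0.8, 1.1 or 1.75 days per week at ICC 0.01, 0.02, 0.05, 0.1, 0.2 or 0.5, against 1.96 × 0.146 = 0.29 from the binomial formula.

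Missing weeks remain a limit. As an assumed example, take a true mean of 3.5 with 20% of weeks unreported. The mean of the reported weeks is (3.5 − 0.2 × 0)/0.8 = 4.4 if those weeks had 0 days, or (3.5 − 0.2 × 2)/0.8 = 3.9 if they had 2. Hence the lower-bound analysis.

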2.5.4 Randomization and Arm Assignment

Patients, cohort 1, will be randomized between arms 1 and 2 stratifying for age. Once randomization of the patient has occurred their parent or primary caregiver, cohort 2, will be directly assigned to the arm in which their child was assigned.

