6.3 POPULATIONS FOR ANALYSES

For the primary outcome of feasibility, all randomized participants will be included. In addition, as described below in section **6.4.2**, we will track total number of eligible individuals approached about the intervention (prior to randomization/enrollment), which will allow us to evaluate the proportion of eligible dyads who enroll. To evaluate exploratory aims, a modified intent-to-treat dataset will be used and will include all participants who, at a minimum, complete the initial in-person training (across EMI and psychoeducation conditions) and questionnaires at Time 1 (baseline) and Time 2 (8 weeks).

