6.4.3 Sub-Group Analyses

As described in section [2.5.3](#), randomization will be stratified by child age for youth ages 5-12, 13-17, and 18-24 years old. Caregivers will be directly assigned to the child's randomization group (i.e., EMI or psychoeducation control). From a feasibility perspective, stratification will allow us to evaluate enrollment/retention data per age group across conditions (reducing the bias associated with enrollment/retention in a single arm treatment study), which will be useful to inform larger RCTs in the future. Stratification across ages will also better allow us to assess exploratory efficacy aims (see [6.4.5](#)) among developmental cohorts.

Further, as described in [6.4.2](#), we will evaluate demographic and medical/disease-related factors that are associated with components of feasibility.

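### The planned Z-test of 8-week retention against 70% can flag only large shortfalls at 10 patients per arm, its direction is inconsistent between sections, and no confidence interval is planned

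*Combined protocol and SAP*

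**What the plan says.** Retention is one of four criteria for the primary feasibility objective. Section 6.1.1 words it as "Treatment specific retention among all randomized participants, with a target retention rate of 70% over the 8 week EMI/control period". Section 6.4.2 gives the method: "A Z-test for binomial proportion with continuity correction will be used to examine whether the retention rate" is below that target. It adds: "Retention rate will be evaluated across the experimental and control groups, and separately for each".

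Other sections bear on how the test is read:

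- **Level and direction.** Section 6.4.1 sets alpha at 0.05 and says "tests will be two-tailed; results will be interpreted in the context of a pilot study in which statistical testing is for descriptive purposes".
- **Role of testing.** Section 6.1 says "The current protocol is a pilot study, and therefore its primary aim does not include hypothesis testing". Section 6.1.1 adds that any tested comparisons within the primary objective are descriptive and hypothesis generating.
- **Analysis set.** Section 6.3 says "For the primary outcome of feasibility, all randomized participants will be included".
- **Unit.** Section 2.5.4 says "Patients, cohort 1, will be randomized between arms 1 and 2 stratifying for age", with caregivers assigned to the patient's arm. Section 6.4.3 agrees. Section 3.1 instead describes dyads as randomized, section 3.4.2 counts each child and each caregiver as a participant, and section 6.4.2 opens with separate parent and child completion rates.
- **Size.** Section 6.2 aims for 10 dyads per arm and states that no sample size determination was made.
- **Replacement.** Section 3.1 allows a patient who comes off study for progression before week 8 and cannot be evaluated to be replaced and left out of the target number.

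Section 6.4 plans percentages for categorical data but no confidence interval.

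**The concern.** The null hypothesis is that retention equals the target. With 10 or 20 observations, failing to reject it is the expected result unless retention is very poor. The p-value therefore carries little information about whether 70% was reached. Over a range of plausible outcomes the observed percentage misses the target while the test is non-significant, and nothing in the plan shows how imprecise the estimate is.

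Section 6.4.2 asks whether retention is too low, which is a one-directional question, while section 6.4.1 makes all tests two-tailed. With so few possible results, that choice moves the cut-off.

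Section 6.4.3 says the enrollment and retention data are meant to inform larger randomized trials. A planner of such a trial needs the estimate and its uncertainty, and this test supplies neither.

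**Working it through.** **Inputs.** Target p0 = 0.70 and continuity-corrected Z-test (6.4.2); alpha 0.05 two-tailed, critical value 1.96 (6.4.1); n = 20 overall and 10 per arm (6.2, with the patient as unit from 2.5.4). The plan states no rejection boundary or power, so there is no figure to reproduce. I use the standard error under the null, which the plan does not specify.

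**1. Cut-offs.** z = (x − 0.7n ± 0.5) / √(n × 0.7 × 0.3), with the correction taken towards zero. The denominator is √4.2 = 2.049 for n = 20 and √2.1 = 1.449 for n = 10. For example, 9/20 gives (9 − 14 + 0.5)/2.049 = −2.196.

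| Retained | z | two-sided p |
|---|---|---|
| 9/20 | −2.196 | 0.028 |
| 10/20 | −1.708 | 0.088 |
| 11/20 | −1.220 | 0.22 |
| 12/20 | −0.732 | 0.46 |
| 13/20 | −0.244 | 0.81 |
| 19/20 | +2.196 | 0.028 |
| 20/20 | +2.684 | 0.007 |
| 3/10 | −2.415 | 0.016 |
| 4/10 | −1.725 | 0.084 |
| 5/10 | −1.035 | 0.30 |
| 6/10 | −0.345 | 0.73 |
| 10/10 | +1.725 | 0.084 |

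A shortfall is significant at 9/20 or fewer and at 3/10 or fewer. At n = 20 the test also rejects upward at 19/20 and 20/20. At n = 10 it never rejects upward, so 4/10 and 10/10 give the same p-value. Results from 10/20 to 13/20 (50% to 65%) miss 70% but are non-significant.

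**2. Chance of flagging a shortfall.** Exact binomial P(X ≤ 9) for n = 20 and P(X ≤ 3) for n = 10. The true rates are assumptions.

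| True retention | Overall | One arm |
|---|---|---|
| 70% | 1.7% | 1.1% |
| 60% | 12.8% | 5.5% |
| 50% | 41.2% | 17.2% |
| 40% | 75.5% | 38.2% |

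**3. Direction.** Read as one-sided at 0.05, the same z-values give p = 0.044 at 10/20 and 0.042 at 4/10, against 0.088 and 0.084 two-sided. Each cut-off rises by one. (With a sample-based standard error, the cut-offs stay at 9/20 and 3/10 either way.)

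**4. Is the normal approximation to blame?** Expected losses per arm at 70% are 10 × 0.30 = 3, below the usual minimum of 5. However, the exact two-sided binomial test gives 0.025 at 9/20, 0.083 at 10/20, 0.011 at 3/10 and 0.076 at 4/10, so the low-side cut-offs are the same. The approximation matters only at the top: 10/10 has exact p = 0.039.

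**5. Unit.** Count children and caregivers as 40 persons and ignore within-dyad correlation. The denominator becomes √8.4 = 2.898. Then 21/40 gives (21 − 28 + 0.5)/2.898 = −2.243, p = 0.025, and 22/40 gives −1.898, p = 0.058. The low-side cut-offs are 21/40 overall and 9/20 per arm. If both members of a dyad always leave together, 10/20 dyads is 20/40 persons, with p = 0.0097 instead of 0.088.

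**6. What an interval would show.** Clopper-Pearson 95%: 14/20, 45.7% to 88.1%; 10/20, 27.2% to 72.8%; 7/10, 34.8% to 93.3%; 4/10, 12.2% to 73.8%.

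**The case against.** The strongest reply is that the plan already concedes the point. It discloses that there was no sample size calculation, labels every test descriptive, and will report percentages. A reader might infer that a non-significant result would be announced as meeting the target. No section says so, and sections 1.1.1 and 6.1.1 simply state a 70% target. A reader might likewise see a contradiction between section 6.1, which disclaims hypothesis testing, and the test in section 6.4.2. The descriptive label in sections 6.1.1 and 6.4.1 largely reconciles the two. Both replies stand. What they leave open is whether this test is a useful description, and step 1 shows that in one arm it is not.

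Three further replies also limit the point:

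- The weakness comes from the sample size and the choice of null, and an exact test would hardly change it. That is correct, and it also means the closing sentence of section 6.4.2 on nonparametric methods would not help, even if it was meant to cover this test.
- The unit is not settled. Treating 20 patients as fixed is the natural reading of section 2.5.4, but sections 3.1, 3.4.2 and 6.4.2 allow others, and under a 40-person count the per-arm figures above no longer apply.
- An interval does not settle the matter either. Those for 10/20 and 4/10 both contain 70%. Reading the target on the observed percentage has its own errors: at a true 70%, it is missed 39% of the time overall (13/20 or fewer) and 35% per arm (6/10 or fewer).

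**Conclusion.** The concern holds in a limited form. With the patient as unit, the two-tailed 0.05 level and the null standard error, the test detects only shortfalls to 45% or below overall and 30% or below per arm. At an assumed true retention of 50% it flags 41% of trials overall and 17% per arm. The conflict between sections 6.4.1 and 6.4.2 on direction is real and alone decides 10/20 and 4/10. The absence of an interval leaves a primary criterion without any statement of precision.

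The documents do not support saying that the plan would pass a failing trial, that the Z approximation is the main fault, or that the denominator is firmly 20. The replacement rule in section 3.1 and the all-randomized set in section 6.3 have not been reconciled. This is a correction worth making to the analysis and reporting of one primary criterion. It does not undermine the pilot.

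**What to change.** In section 6.4.2, replace the Z-test on retention with the count, percentage and exact (Clopper-Pearson) 95% interval, overall and by arm. State that a non-significant p-value will not be reported as meeting the target.

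Name the patient as the unit, and show caregiver and intact-dyad retention separately. Keep all randomized patients in the denominator, as section 6.3 says, and reconcile this with the replacement rule in section 3.1. Do not hard-code 14 of 20 or 7 of 10. Align the randomization wording of section 3.1 with section 2.5.4.

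If a test is kept, make it an exact one-sided binomial test for the overall group only, and make section 6.4.1 agree on direction. With 20 patients it would reject at 10 or fewer (exact level 4.8%); with another denominator the count must be recalculated.

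The cost is a few sentences, with no extra patients or data. The downside is that the intervals are wide and will often include 70%, so they display the imprecision without resolving it.

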- Potential participants will be excluded if there is evidence of pre-morbid severe cognitive or psychiatric disability in parent or child that would impair their capacity for participation, or if there is evidence of clinical disease progression at the time of referral to this study, such that it would prevent the child from engaging in the intervention.

Design

- This is a pilot randomized controlled trial that will compare feasibility and preliminary efficacy of an 8-week EMI group (n=10 dyads) compared to a psychoeducation control group (n=10 dyads).
- All participants will complete measures of feasibility (primary outcome) and exploratory outcomes at baseline and following the 8-week intervention. Exploratory measures will include emotional (e.g., depression, anxiety) and physical (e.g., pain, fatigue) wellbeing, as well as baseline mindfulness/self-compassion.
- The 8-week EMI will consist of one initial in-person session with the child and parent, a series of at-home assignments, and two “booster” sessions. The psychoeducation group will be given educational material about coping with cancer.
- The psychoeducation group will be offered the opportunity to participate in the EMI 8 weeks post-baseline.

TABLE OF CONTENTS

PRÉCIS.....	2
TABLE OF CONTENTS.....	3
STATEMENT OF COMPLIANCE.....	5
1 INTRODUCTION	6
1.1 Study Objectives	6
1.2 Background and Rationale	6
2 ELIGIBILITY ASSESSMENT AND ENROLLMENT.....	9
2.1 Eligibility Criteria	9
2.2 Recruitment Strategies	10
2.3 Screening Evaluation.....	10
2.4 Participant Registration and Status Update Procedures	11
2.5 Intervention Assignment and Randomization/Stratification Procedures	11
2.6 Baseline Evaluation.....	12
3 STUDY IMPLEMENTATION	14
3.1 Study Design	14
3.2 In-person Session	15
3.3 Enhanced Mindfulness Intervention (Immediate Intervention Group).....	17
3.4 Cost and Compensation.....	18
3.5 Off Study Criteria.....	19
4 DATA COLLECTION AND EVALUATION.....	19
4.1 Data Collection.....	19
4.2 Data Sharing Plans	20
4.3 Toxicity Criteria	20
5 NIH REPORTING REQUIREMENTS / DATA AND SAFETY MONITORING PLAN ..	20
5.1 Definitions.....	20
5.2 OHSRP Office of Compliance and Training / IRB Reporting.....	20
5.3 NCI Clinical Director Reporting	20
5.4 NIH Required Data and Safety Monitoring Plan	20
6 STATISTICAL CONSIDERATIONS.....	20
6.1 Statistical Hypothesis	20
6.2 Sample Size Determination.....	21
6.3 Populations for Analyses.....	21
6.4 Statistical Analyses	21

7	HUMAN SUBJECTS PROTECTIONS	23

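### Factors related to home practice are examined only by splitting about 10 EMI patients (or caregivers) at 4 of 7 days, although the days practised are recorded and could be used undivided

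*Combined protocol and SAP*

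**What the plan says.** Section 6.4.2 (Analysis of the Primary Endpoints) states: "A series of t-tests (for continuous variables) and Chi-square tests (for non-continuous variables) will be used to examine potential differences". One of the listed contrasts is "between participants who meet (versus do not meet) the target practice rate (i.e., 4 out of 7 days completed". The same section has a fallback: "Nonparametric models will be used if data do not meet assumption checks".

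The underlying measurement is finer than the contrast. In the weekly text or email described in section 3.2.1, "we will ask individuals to indicate the number of days practiced in the past week". Over 8 weeks this gives each EMI participant up to eight counts between 0 and 7. Section 6.4.2 lists "the number of days practiced (obtained via text/email) by each participant" among the items for descriptive and summary statistics, and names no analysis that relates this number to any factor.

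Section 6.4.3 (Sub-Group Analyses) refers back to 6.4.2: "we will evaluate demographic and medical/disease-related factors that are associated with components of feasibility". The Précis gives the EMI arm 10 dyads. Sections 6.1.1 and 6.4.1 say that tests in this pilot serve description and the generation of hypotheses. Section 6.2 makes no power claim.

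**The concern.** Which families can keep up the practice, and which cannot, is one of the main things a feasibility pilot can teach the next trial. The planned contrast treats a participant averaging 3.9 days a week as the opposite of one averaging 4.0, and as the same as one who never practised. With about 10 people in each role, the split can also leave one side with almost nobody, and then the comparison says nothing. The nonparametric fallback replaces the test but keeps the met/not-met grouping, so it does not recover what the cut discards.

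**Working it through.** The plan states no power, no expected share meeting 4 of 7 days and no effect size for this contrast, so there is no figure of its own to reproduce. The share meeting the target (p) and the true correlation below are assumptions, shown over a range.

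**Inputs from the documents.** 10 patients and 10 caregivers in the EMI arm (Précis); a weekly count of 0 to 7 days (3.2.1); two-sided testing at 0.05 (6.4.1); 70% retention target (6.1.1).

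**1. Information kept by the cut.** For a normal variable cut so that a share p lies on one side, the large-sample efficiency relative to using it undivided is φ(z_p)² / [p(1−p)].

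- p = 0.5: 0.3989² / 0.25 = 0.64, loss 36%
- p = 0.7: 0.3477² / 0.21 = 0.58, loss 42%
- p = 0.8: 0.2800² / 0.16 = 0.49, loss 51%
- p = 0.9: 0.1755² / 0.09 = 0.34, loss 66%

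The figures are symmetric: a share of 20% costs the same as 80%.

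**2. Chance that one group holds 0 or 1 of 10.** Exact binomial, P(X ≤ 1) + P(X ≥ 9).

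- p = 0.5: 22/1024 = 2%
- p = 0.6: 5%
- p = 0.7: 0.121 + 0.028 = 15% (lower tail negligible)
- p = 0.8: 0.268 + 0.107 = 38%
- p = 0.9: 0.387 + 0.349 = 74%

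If only 7 of the 10 give full data, as at the plan's 70% retention target, the chance at p = 0.5, 0.7, 0.8 and 0.9 is 13%, 33%, 58% and 85%.

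**3. Power for a continuous factor, n = 10.** Simulated bivariate normal factor and mean days; a sample with an empty group counts as no rejection. True correlation 0.7:

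| Analysis | 50% meet | 70% | 80% | 90% |
|---|---|---|---|---|
| Spearman on days | 0.58 | 0.58 | 0.58 | 0.58 |
| t-test, met vs not met | 0.41 | 0.36 | 0.29 | 0.19 |
| Ratio | 0.71 | 0.62 | 0.50 | 0.33 |

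A repeat simulation agreed to within 0.02. With a Pearson test on days instead of Spearman, power is 0.68 at correlation 0.7 and 0.33 at correlation 0.5. The split gives 0.21, 0.19, 0.15 and 0.10 at correlation 0.5.

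**4. Binary factors.** In a 2×2 table with n = 10, the smallest expected cell is at most 10 × 0.5 × 0.5 = 2.5, so the chi-square approximation is doubtful in every such table. If the fallback were Fisher's exact test and the factor split 5/5, the smallest attainable two-sided p would be 0.048 at 6/4 meeting/not meeting, but 0.167 at 7/3 and 0.44 at 8/2. From 7/3 onward no data could reach 0.05. An exact rank-sum test on days in the same people can reach 0.008.

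**The case against.** The strongest defence is that the cut is not arbitrary. Four days in seven is what participants are asked to do and is a prespecified feasibility target, so asking who meets it is a fair question. The plan claims no power and presents its tests as descriptive. It also summarises days practised and, under 6.4.4, lists individual data, so with 10 people a reader can see who was just under the target and who was at zero. At a more modest correlation of 0.4, Spearman power is about 0.19 against roughly 0.12 to 0.15 for the split, so neither analysis is informative. For binary factors, the test the plan names is chi-square, not Fisher. Uncorrected chi-square showed about 0.34 power at a 50% share against about 0.33 for rank-sum on days, so there is no visible loss there, although its error rate is unreliable in tables this small.

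Much of this stands, and it limits the weight of the point. It justifies keeping the 4-of-7 count. It does not justify making the split the only way of relating practice to other factors: a descriptive aim is better served by the number that was recorded.

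A reader might infer more: that most of the information is lost, that power is halved, or that one group will often be nearly empty. The documents do not support this, because each statement needs about 80% or more (or 20% or fewer) to meet the target and no expected share is given. Near an even split the loss is about a third and a group of 0 or 1 is rare. Nor can a reader infer that the feasibility conclusions are at risk, since no primary criterion uses this contrast.

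**Conclusion.** The point holds as a free improvement to a secondary analysis. As written, associations with home practice are examined only across a met/not-met split, and the recorded counts are left to description. The cut costs about 36% to 66% of the information as the share meeting the target moves from 50% to 90%, with the power losses and small-group risks shown above.

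These sizes rest on an assumed share, an assumed and strong correlation, and approximate normality of mean days, which in fact are bounded between 0 and 7. They also rest on about 10 people per role. The plan does not say whether control dyads who later take up the EMI would be counted. Pooling patients with caregivers would raise the count, but dyad members are not independent, least of all at ages 5 to 7, where section 3.3.4 has the caregiver share the child's practice. Power stays low even after the change.

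**What to change.** In section 6.4.2, keep the number and percentage meeting 4 of 7 days as a descriptive feasibility count. For associations with demographic, medical and psychological factors, make each participant's mean days practised per week the outcome: Spearman correlation for continuous factors and Wilcoxon rank-sum for binary factors, each reported as an estimate with an interval. Run these separately for patients and caregivers. State how the mean is formed when weekly replies are missing, and whether practice by control dyads who later take up the EMI is included. Keep the statement that the results are hypothesis generating.

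The cost is a few sentences of SAP wording. No new data, visits or participant burden are needed, and the retention, practice and satisfaction targets do not change.
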